1.1 Synopsis

Title:	Non-invasive bioELEctroniC treatment foR pOst-cesareaN (ELECTRON)
Study Description:	This is a randomized trial of 134 individualized post-cesarean delivery who will be randomized to three times use of non-invasive bioelectronic treatment with TrueRelief device or identical appearing sham device for post-cesarean pain management.
Objectives:	Primary : To evaluate whether post-cesarean use of non-invasive bioelectronic treatment reduces inpatient postoperative opioid consumption in morphine milligram equivalents (MME). Secondary : To evaluate whether post-cesarean use of non-invasive bioelectronic treatment 1) improves pain management defined as the presence/absence of moderate to severe pain on post-operative day 2. Moderate to severe pain is defined as a value of 4 or higher on the Brief Pain Inventory worst pain scale (0-10) at discharge, 2) decreases the total amount of opioid tablets prescribed, 3) decreases an opioid refill prescription 4) reduces adverse maternal and infant outcomes.
Endpoints:	Total inpatient opioid consumption in morphine milligram equivalents. Brief Pain Inventory pain severity (worst, least, average, current) in last 24 hours on post-operative day 2, Brief Pain Inventory pain interference during the past week, number of opioid tablets prescribed at discharge, number of opioid prescriptions filled beyond that prescribed at discharge, maternal and infant outcomes.
Study Population:	Individuals with a cesarean delivery who deliver at The Ohio State Wexner Medical Center
Description of Study Intervention:	Non-invasive bioelectronic treatment with TrueRelief device for post-cesarean pain management.
Study Duration:	Recruitment between April 2022 -November 2022. Follow-up, closeout and data analysis by December 2022.
Participant Duration:	6 weeks postpartum

1.2 Schema

1.3 Schedule of Activities

Measure	Visit 0:	Visit 1:	Visit 2:
	Screening & randomization	Discharge	6-wk postpartum in-person or virtual visit
Informed consent	Х		
Demographics	Х		
Medical history	Х		
Randomization	Х		
Number of inpatient opioids used (MME)		Х	
BPI pain severity		X	
Edinburgh Postnatal Depression Scale			Х
Number of opioids prescribed (MME)		Х	
Opioid prescription refilled (or initially filled if not prescribed at discharge)			Х
Opioid-related side effects		X	

ELECTRON Protocol # 2022H0046

Measure	Visit 0:	Visit 1:	Visit 2:
	Screening & randomization	Discharge	6-wk postpartum in-person or virtual visit
Breastfeeding		Х	Х
Maternal & infant outcomes		Х	Х

2 Introduction

2.1 Study Rationale

Cesarean delivery is the most commonly performed major surgical procedure in the United States. Systemic opioids have been universally used for post-cesarean analgesia management, with the number of tablets prescribed varying significantly among providers and institutions. Pain thresholds and analgesic requirements vary among patients, but studies suggest that most women are given prescriptions at discharge for at least 10 more tablets than needed.^{1,2} The consequence of over-prescribing opioids for 1.2 million cesareans annually is at least 12.5 million unused tablets. These unused tablets often go unguarded, and undisposed, providing an important reservoir of opioids that may be misused, diverted or accidentally ingested, contributing to the opioid crisis. Growing recognition of the role that post-cesarean opioid prescribing plays in the opioid crisis has led to a search for alternative methods to control postoperative pain.

2.2 Background

In 2017, approximately 1 in 3 women (32%) in the US gave birth by cesarean delivery.³ More than 80% of women take at least one opioid medication for pain after cesarean.¹ Recent studies show that up to 75% of women who have a cesarean delivery and fill their opioid prescription after their discharge from hospital have unused tablets. The majority of women do not dispose of the excess tablets appropriately.^{2,4-6} These unused opioids are then available for diversion, non-medical use, overdose and development of chronic dependence.

Between 2007 and 2016, the rate of pregnancy-associated mortality involving opioids more than doubled (1.3 to 4.2 per 100,000), as did the percentage of all pregnancy-associated deaths (4% to 10%).⁸ It is becoming clear that opioid overprescribing plays a significant role in maternal mortality. Surgery contributes to the ongoing opioid crisis in two ways. First, opioids provided to treat acute post-surgical pain may lead to chronic opioid use (defined by continued use at 90 days, which occurs in approximately 3-6% of post-surgical patients).^{9,10} 1 in 300 to 1 in 50 opioid-naïve women in the US will develop a persistent opioid use at one year after a cesarean delivery.^{1,11} Secondly, surgeons tend to provide more opioids than patients use postoperatively, leading to excess opioids in a patient's possession. As approximately 60% of adults report that they obtained opioids for nonmedical use from a friend or relative,¹⁰ decreasing the number of excess opioids available to the general population is critical to combating the opioid crisis in the US.

Physicians today struggle to balance the need for adequate control of acute pain after surgery with the desire to limit opioid use and avoid overprescribing, development of dependence and diversion. This had led to a search for effective pain control methods with less short and long-term risks than opioids. The use of multimodal analgesia to control postoperative pain can decrease opioid requirements postoperatively. Multimodal analgesia protocols typically emphasize timed and consistently administered non-opioid analgesics (such as non-steroidal anti-inflammatory drug (NSAIDs) and acetaminophen), with opioid analgesics as needed for breakthrough pain. Use of local treatments and novel devices remains an under-explored adjunct for postoperative pain control as part of a multimodal protocol.

Electrical nerve stimulation represents a promising adjunctive therapy. Originally utilized for chronic pain, transcutaneous electrical nerve stimulation has recently been shown to reduce acute pain and opioid requirements postoperatively, including after total knee arthroplasty and hernia repair.^{12,13} TrueRelief is a novel FDA-cleared bioelectronic device that delivers high-frequency (20,000 Hz) pulsed direct electrical current transcutaneously via stainless steel probes. Efficacy of this technology for pain control after cesarean delivery has not been studied, but it may represent an important adjunct to improve pain control while reducing opioid use.

2.3 Risk /Benefit Assessment

2.3.1 Known Potential Risks

Risks of electroceutical treatment in the postoperative period are minimal. The treatment itself is painless and takes only a few minutes. Treatment with the TrueRelief device or sham device will be administered three times beginning on postoperative day zero until discharge. Aside from the treatment itself, patients will receive usual inpatient care postoperatively, including standard non-opioid and opioid pain medications available as needed.

2.3.2 Known Potential Benefits

Use of the TrueRelief device may improve pain control after cesarean delivery. If treatment successfully decreases opioid requirements, patients may benefit from decreased risk of tolerance, dependence and diversion.

2.3.3 Assessment of Potential Risks and Benefits

As described above, potential risks are not more than encountered in usual care after cesarean delivery. Treatment with the TrueRelief device may improve pain control and reduce opioid requirements.

3. Study Design

This is a blinded randomized trial of 134 individuals undergoing a cesarean delivery who are randomized after cesarean to three times use of non-invasive bioelectronic treatment with TrueRelief device or identical appearing sham device for post-cesarean pain management.

The primary endpoint is the total inpatient morphine milligram equivalents used during hospital admission. The primary hypothesis is that three times use of non-invasive bioelectronic treatment with TrueRelief device decreases the total inpatient morphine milligram equivalents used during hospital admission compared to use with identical appearing sham device. Consenting women will be assigned in a 1:1 ratio to one of the two arms using a secure internet based randomization system. Individuals will be followed through 6 weeks postpartum.

4. Objectives and Endpoints

OBJECTIVES	ENDPOINTS		
Primary			
To evaluate whether non-invasive bioelectronic treatment reduces inpatient post-cesarean opioid consumption.	Total inpatient postoperative opioid consumption in morphine milligram equivalents (MME).		
Secondary			
To evaluate whether non-invasive bioelectronic treatment post-cesarean decreases opioid refill prescriptions.	Opioid prescription filled (beyond that prescribed at discharge) between discharge and six weeks postpartum.		
	Total number of opioid prescriptions filled by six weeks postpartum (beyond that prescribed at discharge).		
To evaluate whether non-invasive bioelectronic treatment post-cesarean decreases the total amount of opioid tablets prescribed at discharge.	Number of opioid tablets prescribed at discharge.		
To evaluate whether non-invasive bioelectronic treatment post-cesarean reduces pain intensity pain scores	Pain severity scores (worst, least, average, current) in last 24 hours assessed on the Brief Pain Inventory numeric scale from 0 to 10 at discharge		
To evaluate whether non-invasive bioelectronic treatment post-cesarean reduces opioid related side effects, wound disruption and increases rates of breastfeeding	 Opioid related side effects including nausea and constipation Surgical site would disruption/infection Breastfeeding rates at discharge and 6 weeks postpartum Maternal depression score ≥ 13 at 6 weeks postpartum 		

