5.4 Strategies for Recruitment and Retention

5.4.1Recruitment Plan

Good recruitment will depend on access, promotion, education and clinical staff buy-in. Research staff will view the daily schedule to review who has had a cesarean. If eligible by medical record review, research staff will approach participants preoperatively or post-operative day 0 to inform them about the study. Randomization should occur on postoperative day 0, but not earlier.

Care providers will be educated about the study via targeted information sessions. It has been found to be helpful to provide in-person informative sessions with specific groups of providers, for example faculty, residents and fellows.

The Ohio State Wexner Medical Center is a large academic medical center with over 5000 deliveries per year. Assuming a 30% rate of cesarean deliveries this is approximately 1500 cesarean deliveries per year. Not every day has 24/7 coverage; therefore it is conservatively assumed that approximately 4 individuals daily are potentially available to enroll on a weekday. It is expected that the number of women who meet the exclusion criteria will be less than 1 percent. Even if 20% of physicians are reluctant to allow their patients to participate (relevant in the setting of private physician deliveries within a hospital) and 60% of women refuse consent for the trial, over 360 women could be enrolled annually.

We are currently conducting a randomized trial in women undergoing cesarean delivery. The aim of the trial is to determine whether an individualized opioid prescription protocol (IOPP) at discharge after cesarean delivery is non-inferior to a prescription for a fixed amount of opioid tablets which approximates current standard of care has similar pain control.

Women are randomized after cesarean delivery and research staff has to be present on day of discharge for randomization. Even with these major barriers to recruitment, sites have been able to recruit approximately 24 participants/ month. While these barriers do not apply to this trial, this study does require a medically trained individual to administer the intervention. Thus the study should conservatively be able to enroll at least 24 participants per month.

6. Study Intervention

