6.1 Study Intervention Administration

6.1.1 Study Intervention Description

Women will be randomized on post-operative day 0 to receive treatments with non-invasive bioelectrical device or identical appearing sham device. Three treatments will be given to each patient. The first treatment should be given as soon as is practical after the cesarean section and not longer than two hours after the procedure. The second treatment will be administered 12 hours after the first treatment, but can be given within a range of 10-14 hours after the first treatment to avoid having to wake the patient when sleeping or otherwise disrupt other care being given to the patient. The third and final treatment will be administered 12 hours after the second treatment, but can be given within a range of 10-14 hours after the second treatment, but can be given within a range of 10-14 hours after the second treatment, but can be given within a range of 10-14 hours after the second treatment, but can be given within a range of 10-14 hours after the second treatment, but can be given within a range of 10-14 hours after the second treatment, but can be given within a range of 10-14 hours after the second treatment to avoid having to wake the patient when sleeping or otherwise disrupt other care being given to the patient when sleeping or otherwise disrupt other care being given to the patient.

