7.1.2 Baseline Procedures

If the patient is eligible and signs the consent form, participants be randomized to TrueRelief device or identical appearing sham device:

In addition to information collected for eligibility, the following information will be obtained from an interview with the participant and/or through the electronic medical record:

- Demographic factors (e.g., maternal date of birth, age, BMI, race/ethnicity, education, employment status, marital status, household income, insurance)
- Factors related to persistent opioid use including tobacco use, history of mental health conditions (e.g., depression, anxiety), use of anti-depressants or benzodiazepines, chronic pain conditions (e.g., back pain, migraines, fibromyalgia).

Medical history including obstetrical outcomes from the current delivery (e.g., indication for cesarean, repeat cesarean, labor prior to cesarean, operative time, type of anesthesia, perioperative complications, gestational age, birth weight, neonatal outcomes).

• Opioid and non-opioid analgesics (e.g., acetaminophen, ibuprofen) use post cesarean through discharge

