8.1 Statistical Hypotheses

The primary endpoint is the amount of inpatient opioid consumed post-cesarean measured by total morphine milligram equivalents used. The null hypothesis is that there is no difference in amount of inpatient MME in the non-invasive bioelectrical device intervention group compared to sham device group. The alternative hypothesis is that the amount of inpatient MME in the non-invasive bioelectrical device intervention group is less then MME in the sham device group.

Key secondary endpoints include:

- Worst pain score assessed at discharge measured by presence or absence of moderate to severe pain at 1 week post-discharge, defined as a value of 4 or more on the BPI worst pain in the last 24 hours numeric scale (0 to 10).
- Opioid prescription beyond that prescribed at discharge within 6 weeks postpartum
- Opioids prescribed at discharge
- Opioid side effects, wound complications and breastfeeding rates

For the secondary endpoints, the null hypothesis is there is no true difference between the two groups. The alternative hypothesis is there is a difference between the groups. For the key secondary outcomes, the level of significance will be adjusted for multiple comparisons using the false discovery rate method.⁴¹

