8.4.2 Analysis of the Primary Endpoint

The primary outcome is continuous and defined as MME consumed inpatient post-cesarean not normally

ELECTRON Protocol # 2022H0046

distributed and cannot be transformed to approximate normality, the Wilcoxon test and the Hodges-Lehmann estimators of the median will be reported. If normally distributed then paired t-test and mean with standard deviations will be reported.

Analysis of Secondary Endpoint

Secondary outcomes that are binary or categorical will be reported as a proportion with relative risk and 95% confidence intervals as appropriate. For normally distributed continuous outcomes, least squares means general linear regression will be used to estimate means and 95% confidence intervals. For continuous outcomes that are not normally distributed and cannot be transformed to approximate normality, the Wilcoxon test and the Hodges-Lehmann estimators of the median will be reported.

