8.4.4 Planned Interim Analyses

No interim analyses are planned given the short duration of enrollment and follow-up.

Subgroup Analyses

Interactions will be evaluated and subgroup analyses conducted to determine whether the effect or lack thereof prevails throughout particular subgroups of participants. The following factors will be considered for subgroup analysis, if there is a significant interaction between the factor of interest and the treatment effect:

- Race/ethnicity
- BMI category (obese vs non-obese)
- Type of labor (labor vs no labor)
- Type of anesthesia
 - General, spinal, combined spinal-epidural, epidural
 - Neuraxial morphine administration
- Skin incisional type (low transverse vs vertical midline)
- Primary vs repeat cesarean

• Time from delivery to discharge (<48 hours, \geq 48 hours).

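### The primary opioid endpoint has two conflicting windows and neither starts at randomization, so doses given before assignment can be counted as outcome; the cost is added variance, not bias

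*Combined protocol and SAP*

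**What the plan says.** The combined protocol and SAP describes the window for the primary endpoint in two ways.

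- **Whole admission.** Section 3 (Study Design): "The primary endpoint is the total inpatient morphine milligram equivalents used during hospital admission". The primary hypothesis in the same section repeats that window.
- **After surgery.** Section 4: "Total inpatient postoperative opioid consumption in morphine milligram equivalents (MME". Section 8.1: "The primary endpoint is the amount of inpatient opioid consumed post-cesarean measured by total morphine milligram equivalents used". Section 8.4.2: "The primary outcome is continuous and defined as MME consumed inpatient post-cesarean". The primary objective in Section 1.1 also says postoperative, although the endpoint row there gives no start point.

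Section 7.1.2 collects the data as one undivided block: "Opioid and non-opioid analgesics (e.g., acetaminophen, ibuprofen) use post cesarean through discharge".

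On timing, Section 5.4.1 says: "Randomization should occur on postoperative day 0, but not earlier". Section 6.1.1 adds: "The first treatment should be given as soon as is practical after the cesarean section and not longer than two hours after the procedure". Section 9.1.1 lets women be approached up to 24 hours after the cesarean. No section starts the count at randomization or at first treatment, and none excludes earlier doses.

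**The concern.** A dose given before assignment cannot respond to the device. The admission window, taken literally, brings in labor, intraoperative and neuraxial opioids. The postoperative window brings in whatever is given between the end of surgery and randomization.

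The population makes the first case matter. The subgroup list in Section 8.4.4 covers labor and no labor, general and neuraxial anesthesia, and "Neuraxial morphine administration". Opioid exposure before randomization could therefore differ widely between women for reasons unrelated to the device.

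Two things are at stake. The same woman can have two different primary outcome values depending on the section followed, which leaves the analyst a choice that could be made after seeing data. Any early doses counted also add noise to a trial sized with no allowance for it: Section 8.2 gives the bare number for 90% power and mentions no dropout margin.

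**Working it through.** **Inputs.** Section 8.2 gives a control mean of 42 MME and SD 15 over postoperative day 0 to 2, a 20% reduction to 33.6, 90% power, and 67 per arm. The difference is 42 − 33.6 = 8.4 MME. Neither alpha nor sidedness is stated; I assume two-sided 5% because that reproduces the sample size (one-sided 5% gives 110 in total). Power is for a t-test on two independent arms.

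**Step 1: the plan's own figure.** By the normal formula, n per arm = 2 × (1.960 + 1.282)² × 15² / 8.4² ≈ 67.0, so 134 in total (136 if 67.01 is rounded up). For the t-test, the noncentrality is 8.4 / (15 × √(2/67)) = 3.24 and power at 67 per arm is 89.6%. The stated figure is reproduced.

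**Step 2: what early doses do to the difference.** Write each woman's total as E (before randomization) plus L (after). Randomization gives E the same expectation in both arms, so the expected difference in totals equals the expected difference in L. Counting E leaves the absolute difference unchanged. It raises the variance (to Var(E) + Var(L) if the two are independent) and enlarges the denominator of the percentage reduction.

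**Step 3: postoperative window, two-hour limit kept.** The documents do not say how much of the 42 MME falls before randomization. Assume even use over 48 hours: 42 × 2/48 = 1.75 MME. Assume also an independent SD of 2.5 for that amount, and that the device cuts only later doses by 20%. The difference is 0.20 × (42 − 1.75) = 8.05 MME.

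| Count | SD | Power |
|---|---|---|
| Early doses included | 15 | 86.9% |
| From randomization | √(15² − 2.5²) = 14.79 | 87.8% |

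Moving the start point gains about one percentage point. Over 72 hours the early amount would be 42 × 2/72 = 1.17 MME, so the stake is smaller still.

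**Step 4: Section 3 window read literally.** Opioids from labor and surgery come on top of the 42 MME. The expected difference stays at 8.4, and SD = √(15² + s²), where s is an assumed independent SD of the added amount. The added means are also assumed.

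| Added mean; SD s (assumed) | Total SD | Percentage reduction | Power |
|---|---|---|---|
| none | 15.0 | 8.4/42 = 20.0% | 89.6% |
| 5; 5 | 15.8 | 8.4/47 = 17.9% | 86% |
| 10; 10 | 18.0 | 8.4/52 = 16.2% | 76% |
| 20; 15 | 21.2 | 8.4/62 = 13.5% | 62% |

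Power depends only on s, not on the added mean. The documents give no value for either.

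**The case against.** The strongest reply is that this is one stray phrase. The Section 1.1 objective and Sections 4, 8.1 and 8.4.2 all say postoperative or post-cesarean, and Section 7.1.2 lists analgesic use only from the cesarean onward. Table 1 has conversion factors only for hydrocodone and oxycodone, so neuraxial or parenteral opioids could not be converted from it. The planning mean covers postoperative day 0 to 2, early hours included, so the 8.4 MME may already be net of doses the device cannot reach. Starting at the end of surgery is a defensible choice, and Section 8.4.3 adjusts for imbalance in key pre-treatment risk factors.

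Most of this stands as a limit on size. It makes the postoperative reading the likelier intention and the loss under it small. It does not remove the conflict: Section 3 uses the admission window in both endpoint and hypothesis, and Table 1 does not say that opioids it omits go uncounted.

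A reader might go further and infer that early doses dilute the treatment effect. If 5 or 10 of the 42 MME preceded randomization, the difference would be 0.20 × 37 = 7.4 or 0.20 × 32 = 6.4 MME, and power at SD 15 would be 81% or 69%. Those losses come from assuming a smaller treatable total. Counting from randomization leaves the same 7.4 or 6.4 MME and, at SD 15, the same power, so they do not measure the effect of the window. Amounts that large also fit poorly with a two-hour gap: by Table 1 one 5 mg oxycodone tablet is 5 × 1.5 = 7.5 MME, so a mean of 10 would need more than one tablet per woman before randomization.

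**Conclusion.** The point holds as a conflict in the definition of the primary endpoint, with a start time that is not tied to randomization. It does not hold as bias in the absolute MME difference, and a chance imbalance in early doses is covered by the test's error rate.

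The size depends on which section is followed. Under the postoperative reading with the two-hour limit kept, the cost is about one percentage point of power, given the assumed 1.75 MME (SD 2.5). Under the literal Section 3 reading it runs from slight to serious, from about 86% down to about 62% power for added SDs of 5 to 15 MME. That range is illustrative. All these figures assume that early and later use are independent.

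The short gap relies on the two-hour limit in Section 6.1.1, which does not fit the 24-hour approach window in Section 9.1.1.

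**What to change.** Use one definition in Sections 1.1, 3, 4, 8.1 and 8.4.2: MME of opioids administered from randomization to discharge. State that labor, intraoperative and neuraxial opioids, and any other dose timed before randomization, are not counted. In Section 7.1.2, split the analgesic record at the time of randomization: doses from the cesarean to randomization become a baseline value, available as a prespecified covariate, and later doses form the outcome. Reconcile the first-treatment limit in Section 6.1.1 with the approach window in Section 9.1.1.

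The cost is protocol wording and summing doses from timed administration records. No visit or procedure is added. The planning mean of 42 may need a slight downward restatement, because doses before randomization drop out.

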5. STUDY POPULATION

5.1.1 Inclusion Criteria

In order to be eligible to participate in this study, an individual must meet all of the following criteria: Post cesarean delivery (combined vaginal/cesarean deliveries are not eligible)

Singleton, or twin gestation

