5.1.2 Exclusion Criteria

An individual who meets any of the following criteria will be excluded from participation in this study:

- Fetal or neonatal death prior to randomization
- Inability to randomize on postoperative day 0
- Inability to complete all three non-invasive bioelectronic treatment during inpatient stay as assessed by research staff
- Language barrier (non-English or Spanish speaking)

• Participation in another intervention study that influences the primary outcome in this trial

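### Women on daily opioids before delivery are eligible and their pre-existing use is not recorded at baseline, so ongoing oxycodone or hydrocodone and its renewals can count in the MME and opioid-fill endpoints

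*Combined protocol and SAP*

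**What the plan says.** **Eligibility.** Section 5.1.1 asks for a singleton or twin gestation and "Post cesarean delivery (combined vaginal/cesarean deliveries are not eligible"). It has no opioid-naive requirement. Section 5.1.2 opens with "An individual who meets any of the following criteria will be excluded from participation in this study" and lists five items: fetal or neonatal death, inability to randomize on day 0, inability to complete the three treatments, language, and another intervention study. None concerns opioid use. Section 5.4.1 adds: "It is expected that the number of women who meet the exclusion criteria will be less than 1 percent". The population is meant to be almost unselected.

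**Endpoints.** Section 3 states: "The primary endpoint is the total inpatient morphine milligram equivalents used during hospital admission". Section 4 gives "Total inpatient postoperative opioid consumption in morphine milligram equivalents (MME") for the primary objective. It gives two fill endpoints: "Opioid prescription filled (beyond that prescribed at discharge) between discharge and six weeks postpartum" and "Total number of opioid prescriptions filled by six weeks postpartum (beyond that prescribed at discharge"). No endpoint text sets aside opioid that the woman was already taking. Section 6.1.1.1 converts opioid use to MME, and its Table 1 has factors for hydrocodone and oxycodone only.

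**Baseline.** Section 7.1.2 collects factors related to persistent opioid use, among them "chronic pain conditions (e.g., back pain, migraines, fibromyalgia"). Opioid use before admission is not on the list; the only opioid item covers the period from the cesarean to discharge.

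**Design and analysis.** Prior opioid use is not a randomization stratum (6.2), a named covariate (8.4.3) or a subgroup factor (8.4.4).

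**The concern.** The objectives concern post-cesarean opioid need and refills. For a woman who takes oxycodone or hydrocodone every day, the endpoints as written also record her usual dose and its renewals, whatever the device does. A few such women could add large values to inpatient MME. A continuing prescription could also make a fill event likely in either arm.

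The plan expects women with chronic pain, because it collects that history, but it does not ask for the variable that would identify this contribution. The adjustment in 8.4.3 can work only on a factor that was recorded. What is at stake is how cleanly the endpoints measure their objectives, and some precision.

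**Working it through.** **1. The plan's own figure.** Section 8.2 gives means 42 and 33.6 (difference 8.4), SD 15, 90% power and 134 women. Alpha is not stated there; two-sided 0.05 is assumed.

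Total N = 4 × [15 × (1.960 + 1.282) / 8.4]² = 134.0.

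At 67 per arm the power is 90.0% (normal) or 89.6% (t). One-sided 0.05 gives 110 and does not fit. The sample size agrees with its inputs.

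**2. Chance of enrolling such women.** Prevalence r is not in the documents. P(at least one in 134) = 1 − (1 − r)^134:

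| r | P(at least one) | Expected number |
|---|---|---|
| 1% | 74% | 1.34 |
| 2% | 93% | 2.68 |
| 5% | 99.9% | 6.7 |

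**3. Effect on a mean.** One woman with an assumed extra 150 MME moves her arm's mean by 150/67 = 2.2 MME. That is 2.2/8.4, or about 27% of the target difference.

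**4. Mean-based power, fixed extra E per stay.** SD = √(15² + r(1 − r)E²), with the difference held at 8.4 and 67 per arm:

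| r | E (MME) | SD | Power |
|---|---|---|---|
| 1% | 60 | 16.1 | 85% |
| 1% | 120 | 19.2 | 72% |
| 2% | 60 | 17.2 | 81% |
| 2% | 120 | 22.5 | 58% |
| 5% | 60 | 19.9 | 69% |
| 5% | 120 | 30.1 | 36% |

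**5. t-test against Wilcoxon.** Simulation with 4,000 trials per setting: normal values with the plan's means and SD, truncated at 0, and each woman with probability r gaining a uniform extra amount; two-sided 0.05. Repeat runs differ by up to about three points.

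| Setting | t-test | Wilcoxon |
|---|---|---|
| None | 90% | 88–89% |
| 1%, extra 100–200 MME | about 64% | 86–88% |
| 2%, extra 100–200 MME | about 51% | 85–86% |
| 1%, extra 200–600 MME | about 43% | about 87% |
| 2%, extra 200–600 MME | about 23% | 85–86% |

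At 5% prevalence Wilcoxon power is about 79–81%.

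**6. Which test would be used.** Section 8.4.2 sends MME to Wilcoxon and Hodges-Lehmann if it is not normal and cannot be transformed. It names no normality test. If a Shapiro test on arm-centred values is assumed, normality is rejected in essentially every trial that contains a woman with an extra 100 MME or more. Power under that rule is 90% with none, and about 85–88% at 1–2%. Transformation was not modelled.

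**7. Fill endpoint.** The plan gives no rates. Take 30% against 10% for illustration, and make every such woman an event: p′ = p(1 − r) + r.
- r = 1%: 30.7% and 10.9%; relative risk 2.82 instead of 3.00; power 83% instead of 85%.
- r = 2%: 31.4% and 11.8%; relative risk 2.66; power 81%.

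**The case against.** The strongest reply is that little follows for the primary test. A few extreme values make MME visibly non-normal, 8.4.2 then leads to a rank test, and power drops by only a few points. Section 8.4.1 also summarizes non-normal data by medians. This stands. A reader might infer from the t-test column that the trial loses much of its power; the plan's own decision rule does not support that.

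Second, Section 8.2 takes SD 15 from a review of the hospital's own patients and states no opioid-naive restriction. With 1% of women and an extra 100–200 MME, the added variance is 0.01 × 23,333 − (0.01 × 150)² = 231, more than the whole planned variance of 225. If the review covered all comers, that scenario does not fit SD 15, and any real effect is already in the sample size. This stands as a limit on the size.

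Third, a reader might infer that maintenance treatment for opioid use disorder is counted in full. Table 1 does not establish that. An agent outside it has no stated factor, so the text neither counts it nor leaves it out.

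Fourth, the baseline list is introduced as non-exhaustive, and Section 4's objective speaks of refills, which may mean refills of the discharge prescription only. Both are possible readings. Neither puts pre-admission opioid use on the form or takes a continuing prescription out of the fill definition.

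Finally, broad eligibility is a legitimate choice. That is true, but the plan should make it openly and say how these women's opioid is handled.

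**Conclusion.** The gap is in the text. Women on daily opioids are eligible, their prior use is not a listed baseline item, chronic oxycodone or hydrocodone enters total inpatient MME, and continuing prescriptions can enter the fill endpoints. The treatment of maintenance agents in MME is undefined.

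It would go too far to read this as bias in favor of one arm. Allocation is randomized 1:1 and analysis is by assigned group (8.3), so these women are balanced in expectation. The harm is added noise, chance imbalance in a trial of 134, and endpoints that partly measure something other than their objectives.

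The size is modest for the primary test: about 88–90% power falling to 85–88% at 1–2% prevalence, and to 79–81% at 5%. Large losses arise only if means are compared by t-test. The fill endpoint moves little at 1–2% under the illustrative rates, but no rank test protects it. Prevalence, extra dose and fill rates are all assumptions. This is a low-cost improvement in endpoint validity, not a flaw that undermines the trial.

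**What to change.** 1. Record pre-admission opioid use (agent, and whether daily or maintenance) at screening, and add it to the 7.1.2 list.
2. Add to 5.1.2 an exclusion for chronic or maintenance opioid therapy at delivery, with the sponsor's working definition.

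If the sponsor prefers to keep these women:
- prespecify pre-admission opioid use as a covariate, or as a stratum in a stratified Wilcoxon test on the rank branch;
- add a sensitivity analysis of MME and fills without these women;
- do not count continuation of a pre-delivery prescription as a fill event;
- state whether and how agents outside Table 1 enter MME.

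Counting only opioid newly ordered for post-cesarean pain should not be the main remedy. It is hard to apply when the same oxycodone serves both purposes, and it would bring misclassification.

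**Cost.** One criterion and one record-review item. Applicability narrows slightly, and a few eligible women are lost from about 1,500 cesareans a year (5.4.1). No participant's treatment changes.
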